## \*Please add a Study Contact [name] [name] The Study Contact(s) will receive all important system notifications along with the Principal Investigator. (e.g. The project contact(s) are typically either the Study Coordinator or the Principal Investigator themselves). **VASDHS IRB Human Subjects Protocol** v20190121 **Section 1 - Preliminaries** Principal Investigator: [name] Protocol Title: Feasibility Testing of Transpelvic Magnetic Stimulation as a Novel Intervention to Improve Urogenital Function in Prostate Cancer Survivors IRB Protocol Number: H200110 Protocol Nickname: Magnetic Stimulation - Human Form Template Version: v20150115 Date Prepared:

Please be advised that this protocol application form has changed as a result of the 2018 Common Rule. There are new questions and sections, and you may be required to provide additional information to

08/03/2020

YesNo

previous sections.

O I don't know

1b) Please select:

1a) Is this study considered human research?

This is a revision of an existing protocol

Was this study initially approved prior to January 21, 2019?

This is an application for a NEW human subject research protocol

Were you instructed to convert to the 2018 Common Rule Requirements?

Section 2 - Research Subjects	
2a) What is the total planned number of VA-consented subjects?	
Include the total number of subjects who will prospectively agree to participate in the study (e.g., documented consent, oral consent, or other).	
2b) What is the total number of VA subjects who WILL NOT be consented?	
Include the total number of subjects that will be included without consent (e.g., chart review). Note: Data about people are still considered "human subjects" by the IRB, so even if you do not intend to contact the patients whose charts you will review, you still should enter the number of charts as your "planned subjects."  0	
Section 2.1 Consented Subject Groups	
2.1) For each of the subject categories listed below, indicate whether or not these subject group participate in the study:	ps will
2.1a) Children under the age of 18  Note: If neonates or children will be involved in this study, certification by the Medical Center Director will be required. Only minimal risk research may be performed with children. Only non-invasive monitoring and/or prospective observational and retrospective record review studies that are minimal risk can be conducted in VA involving neonates.	
O Yes O No	
2.1b) Pregnant women	
O Yes O No	
2.1c) Individuals with cognitive/decisional impairment	
O Yes ⊙ No	
2.1d) Non-English-speaking individuals	
O Yes ⊙ No	
2.1e) Prisoners of War (explicitly targeting this group)	
O Yes ⊙ No	
2.1f) Non-Veterans (Note: Justification for inclusion of non-Veterans will be required)	
O Yes O No	
2.1g) Incarcerated individuals (Note: VA CRADO approval will be required)	
O Yes ⊙ No	
2.1h) VA employees - including VA paid, IPA, or WOC (Note: Union review and authorization may be required)	
O Yes O No	
2.1i) Students of the institution (e.g., resident trainees) or of the investigator	
O Yes ⊙ No	
2.1j) Patients with cancer (or high cancer risk) [explicitly targeting this group]	
• Yes • No	

### Section 3 - Study Features (these items default to "No" for convenience)

3) This section consists of several Yes/No questions addressing protocol characteristics. Click on Save and Continue.

### **Section 3.1 Protocol Basics**

Select all that apply	
3.1a) The research intends to change the participant.	
⊙ Yes ○ No	
3.1b) Interactions with living participants to collect data or specimens with no intent to change them.	
O Yes ⊙ No	
3.1c) This is a study that never has any subject contact and does not collect subject identifiers	
O Yes O No	
3.1d) This is a chart review study involving retrospective or prospective medical records.	
O Yes O No	
3.1e) This is a multi-site study occurring in-part or in-full at other locations.	
O Yes    No	
3.1f) There is an international component to this research. International research includes sending or receiving human derived data or specimens (identifiable, limited data set, coded, or deidentified) to or from an international source. International research does not include studies in which VA is only one of multiple participating sites where the overall study-wide PI is not a VA investigator.	
O Yes O No	
3.1g) This study includes off-station activity (not including VA-leased space or CBOC clinics) conducted under VASDHS IRB approval. Note: this does not include research conducted by a collaborator at their home institution under their institutional approval.	
O Yes O No	
3.1h) VA subjects will participate in part or in full at other locations (not including VA-leased space or clinics) under VASDHS IRB approval. Note: if this study involves remote participation of subjects, please indicate "no" and describe their remote participation in section 9 of the application. This question is intended to understand whether participants must physically go to a non-VA location to participate in this VA research study.	
C Yes ⊙ No	
Section 3.2 Specimen Use and Data Repository	
Indicate whether or not each of the following applies to this protocol	
3.2a) Involves specimens that are left over from pathological or diagnostic testing (non-research specimens)	
O Yes O No	
3.2b) Involves specimens collected for research purposes only	
O Yes O No	
3.2c) This study includes specimen banking (specimens are retained for use outside of the purposes of this protocol)	

O Yes O No
3.2d) The study involves DNA genotyping or other genetic analysis
O Yes ⊙ No
3.2e) Biological specimens/material will be sent outside of the VA.
O Yes ⊙ No
3.2f) A data repository is maintained (data are retained after completion of the protocol for other uses, IMPORTANT: see ? before checking "yes")
O Yes ⊙ No
3.2g) Data will be shared outside of the VA (identifiable, coded, limited data set, or deidentified)
O Yes ⊙ No
Section 3.3 Treatment and Clinical Trials
Indicate whether or not each of the following applies to this protocol
3.3a) Includes a treatment component (a research treatment)
⊙ Yes ○ No
3.3b) Study is a clinical trial. Note: A clinical trial is a research study in which one or more human subjects are prospectively assigned to one or more interventions (which may include placebo or other control) to evaluate the effects of the interventions on biomedical or behavioral health-related outcomes.
⊙ Yes ○ No
3.3c) Has a data safety monitoring board ( DSMB ) or data safety monitoring committee.
O Yes ⊙ No
3.3d) Has a data safety monitoring plan (but not a DSMB) (this is not the data security plan, it is a safety plan).
⊙ Yes ○ No
Section 3.4 Drugs and Devices
Indicate whether or not each of the following applies to this protocol
3.4a) Drugs that require FDA action such as an Investigational New Drug (IND) approval or exemption or 510 (k) approval.
O Yes ⊙ No
3.4b) Other drugs, supplement, etc. that do not require FDA action for inclusion in the study.
O Yes ⊙ No
3.4c) Medical devices requiring FDA IDE approval or waiver
⊙ Yes ○ No
3.4d) Other medical devices
● Yes ○ No

Indicate whether or not each of the following applies to this protocol	
3.5a) Study places subjects at greater than minimal risk (do not include risks that are due to standard care)  O Yes   No	
3.5b) Human subjects are exposed to radioisotopes (do not include standard care).  ○ Yes   ○ No	
3.5c) Subjects have other radiation exposure (e.g., x-rays) (do not include standard clinical use).  ○ Yes ○ No	
3.5d) Target population has psychiatric diagnosis, behavioral complaint, or chronic pain.  O Yes   No	
Section 3.6 Clinical Facilities and Standard Care	
Indicate whether or not each of the following applies to this protocol	
3.6a) Study uses VA clinical services (e.g., adds required tests run in the VA lab for study purposes; research procedures concurrent with clinical care)  • Yes • No	
3.6b) Includes procedures or drugs that will be considered part of standard care.	
C Yes     No	
3.6c) Involves lab tests done for research purposes.	
O Yes   ● No	
O Yes    No  Section 3.7 Subject Expenses and Compensation	
Section 3.7 Subject Expenses and Compensation	
Section 3.7 Subject Expenses and Compensation  Indicate whether or not each of the following applies to this protocol  3.7a) There may be expense or added costs to the subject or the subject's insurance.	
Section 3.7 Subject Expenses and Compensation  Indicate whether or not each of the following applies to this protocol  3.7a) There may be expense or added costs to the subject or the subject's insurance.  Yes No  3.7b) This is a qualifying cancer treatment trial and subjects may be billed for study drugs or procedures.	
Section 3.7 Subject Expenses and Compensation  Indicate whether or not each of the following applies to this protocol  3.7a) There may be expense or added costs to the subject or the subject's insurance.  Yes No  3.7b) This is a qualifying cancer treatment trial and subjects may be billed for study drugs or procedures.  Yes No  No  3.7c) This is a cancer treatment trial but subjects will not be billed for study drugs or procedures.	
Section 3.7 Subject Expenses and Compensation  Indicate whether or not each of the following applies to this protocol  3.7a) There may be expense or added costs to the subject or the subject's insurance.  Yes No  3.7b) This is a qualifying cancer treatment trial and subjects may be billed for study drugs or procedures.  Yes No  3.7c) This is a cancer treatment trial but subjects will not be billed for study drugs or procedures.  Yes No	
Section 3.7 Subject Expenses and Compensation  Indicate whether or not each of the following applies to this protocol  3.7a) There may be expense or added costs to the subject or the subject's insurance.  Yes No  3.7b) This is a qualifying cancer treatment trial and subjects may be billed for study drugs or procedures.  Yes No  3.7c) This is a cancer treatment trial but subjects will not be billed for study drugs or procedures.  Yes No  3.7d) Subjects will be compensated (either in cash or other means such as a gift certificate).	
Section 3.7 Subject Expenses and Compensation  Indicate whether or not each of the following applies to this protocol  3.7a) There may be expense or added costs to the subject or the subject's insurance.  ○ Yes  No  3.7b) This is a qualifying cancer treatment trial and subjects may be billed for study drugs or procedures.  ○ Yes  No  3.7c) This is a cancer treatment trial but subjects will not be billed for study drugs or procedures.  ○ Yes  No  3.7d) Subjects will be compensated (either in cash or other means such as a gift certificate).  ○ Yes  No	
Section 3.7 Subject Expenses and Compensation  Indicate whether or not each of the following applies to this protocol  3.7a) There may be expense or added costs to the subject or the subject's insurance.  Yes No  3.7b) This is a qualifying cancer treatment trial and subjects may be billed for study drugs or procedures.  Yes No  3.7c) This is a cancer treatment trial but subjects will not be billed for study drugs or procedures.  Yes No  3.7d) Subjects will be compensated (either in cash or other means such as a gift certificate).  Yes No  Section 3.8 Subject Activities	

3.8b) Includes the use of recruitment materials such as flyers, advertisements, or letters	
C Yes O No	
3.8c) Involves facial photographs or audio or video recordings of patients	
O Yes ⊙ No	
Section 3.9 Sponsors and Collaboration	
Indicate whether or not each of the following applies to this protocol	
3.9a) This research is a funded research project (commercial (industry) sponsor, NIH, VA, other).	
⊙ Yes ○ No	
3.9b) Other commercial (industry) non-financial support is provided (e.g., drugs or supplies).	
○ Yes • No	
3.9d) The protocol has Department of Defense involvement (e.g., subjects or funding).	
O Yes ⊙ No	
3.9c) The PI or other study staff member has a financial interest or other real or potential conflict related to this study.	
○ Yes • No	
3.9e) This study involves collaborative research activities (research conducted at other institutions under the authorities or approvals of the other institution/s). Note: this may include other VA and/or non-VA institutions, but does not include off-site VA research.	
O Yes O No	
Section 4 - Estimated Duration	
4) What is the estimated duration of the entire study? (From IRB approval to IRB closure)	
3 years	
Section 5 - Lay Language Summary	
5) Provide a summary or synopsis of the proposed study using non-technical language (not moparagraph)	re than 1
The overall purpose of this project is to improve the quality of life of prostate cancer survivors. Prostate cancer is most common in men over 50 years. With early diagnosis, patients can pursue potentially curative interventions that include surgical procedures. These surgical treatments lead to sexual dysfunction and leakage of urine. Although it is recognized that bladder control and sexual functions are important issues affecting quality of life, there has been only limited research into methods to prevent these forms of dysfunctions in cancer survivors. We are proposing a new preventive strategy using magnetic stimulation to strengthen the muscles that are responsible for maintaining these functions.	
Section 6 - Specific Aims	
6) Provide a statement of specific aims and hypotheses that serve as the basis for this protocol. those aspects that justify the use of human subjects.	Emphasize

1) To show feasibility of recruitment of prostate cancer survivors, acceptability of transpelvic

magnetic stimulation (TPMS) intervention and retention of this Veteran population.

- 2) To test the feasibility of administering symptom scores in this population to detect severity and early recovery of functional impairment.
- 3) To test the feasibility of diagnostic imaging to establish: penile/pelvic floor muscle (PFM) blood flow, PFM anatomical and morphological changes before surgery, immediately after surgery, and after TPMS interventions.

### Section 7 - Background and Significance

### 7) Provide a succinct discussion of relevant background information to justify performing the proposed study.

Literature suggests that prostate cancer is the most common type of cancer in men over 50 years old, with an estimated 218,000 new cases each year. This cancer's incidence is especially prevalent (29%) among VA patients . Surgical therapy for prostate cancer is a significant risk factor for urogenital complications which dramatically affect the quality of life for male Veterans, such as erectile dysfunction (ED), or the inability to initiate or maintain adequate erection for intercourse, and urinary incontinence 20-80% of these men will never regain normal erectile function and 31% will have urinary incontinence. Transpelvic magnetic stimulation (TPMS) for Urogenital and Pelvic Floor Disorders: Recently, TPMS therapy has been recognized as beneficial in treating nerve and muscle injuries. TPMS acts by strong pulsing magnetic fields that depolarize neural elements, resulting in improved muscle contraction. Repetitive contraction and relaxation of normal skeletal muscle results in increased muscle strength, endurance, and circulation. Previous studies showed beneficial effects of TPMS in UI in females. However, these studies were inconclusive. Apparently, these clinical studies attempted to reverse the established neuropathy and muscle dysfunction in symptomatic patients. Our proposed studies will evaluate the preventive potential of TPMS in acute neuropraxia related penile and sphincter muscle dysfunction. Recent reports showing efficacy of TPMS for skeletal muscle regeneration after surgical trauma clearly supports our claim. TPMS does not cause adverse effects but improves muscle function by minimizing post-injury inflammation, atrophy and scar formation. Based on published reports and taking advantage of muscle regeneration potential, we propose TPMS after surgery (as acceptable to the urologic surgeon) to enable systematic evaluation of its potential to prevent muscle dysfunction, i.e., immediate muscle recovery prior to fibrosis onset (never attempted before). Furthermore, TPMS treatment will lead to muscle strengthening. In addition, low intensity (5-10% amplitude) TPMS improves blood flow as shown in our laboratory (AUA 2018 oral presentation by Kim, et al- TRANSPELVIC MAGNETIC STIMULATION (TPMS) AS A NOVEL THERAPY TO ENHANCE PENILE MICRO AND MACRO CIRCULATION, J Urology, Vol. 199, No. 4S, Supplement, Saturday, May 19, 2018), and higher intensity (30-50% amplitude-based on the amplitude that results in patient feeling the muscle activity) helps muscle regeneration and function by minimizing post-injury inflammation, atrophy and scar formation. Based on these observations, we hypothesize that TPMS: (a) will prevent pelvic floor muscle atrophy and result in improved strength and (b) will decrease muscle fibrosis by improving penile and pelvic muscles blood flow leading to accelerated recovery after injury. TPMS has been employed as a nonsurgical intervention for stress UI in females since 1998. For treatment with TPMS, an embedded magnetic coil positioned on the chair generates pulsed electromagnetic fields that can penetrate into the pelvic floor muscles, leading to nerve stimulation and muscle contractions. Pelvic floor muscle blood flow can be non-invasively measured simultaneously using Doppler probe placed on the penile skin as is done routinely for clinical diagnosis. Pelvic floor muscle changes can be non-invasively measured by MR imaging. The proposed mechanism is to increase pelvic muscle strength and endurance through repetitive contractions. Proposed TPMS may result in increased urethral pressure and may strengthen muscles to prevent venous leak. Non-invasive TPMS has several advantages and has never been tried in post-prostatectomy patients.

Recently, application of neuromodulation using **repetitive magnetic stimulation** (rMS) has shown to be a safe, effective, and preferred approach of treatment for muscular and neurological injuries of several conditions, including urinary incontinence as it is non-invasive and relatively pain free. In addition, rMS displays potential to improve blood flow, muscle regeneration and function by minimizing post-injury inflammation, atrophy and scar formation .

We plan to use MagVenture R30 device and associated coils/paddles for which we are attaching 510Ks, users manual and brochures. In addition, please see online link: https://www.magventure.com/en-gb/Products/MagPro-magnetic-stimulators/MagPro-R30 for more details.

All parameters are within the FDA approved range for pulse frequency, amplitude and duration. Magnetic stimulation device MagVentrure's R30 (FDA approved for peripheral stimulation) that targets pelvic floor muscles will be used. We propose 10 Hz (for blood flow stimulation) and 30

Hz (for pelvic muscle strengthening), in an 8 seconds on- 4 seconds off pulsing manner TPMS that encompass previously employed range of frequencies in humans for pelvic floor stimulation (based on published methodology -Lim et al, J Urol 197:1302, 2017, attached). Number of trains will be about 50. no of pulses in train would be about 240. Each cycle will be of total 20 minutes duration, followed by 20 min of coil cooling period before the second cycle. Based on our preliminary studies in 2 subjects for about 8 weeks, this protocol was well toleated. Both subjects felt the sensations at the high frequency 30 Hz. In these preliminary studies performed in two cancer surivors using a previously approved protocol, we observed a significant improvement in continence function (number of pads used) after 4 -6 weeks of TPMS.

### Section 9 - Design and Methods

9) Describe the research design and the procedures to be used to accomplish the specific aims of the project. Provide a precise description of the planned data collection (include what systems or databases will be used/accessed to gather data), analysis and interpretation. For chart review studies, include the timeframe of collection. Address sample size, inclusion of women and minorities. Define in clear terms exactly what will be done to the human subjects.

This is a previously approved protocol-*H180085-* "Development of a Novel Method to Strengthen Pelvic Floor Muscles Using Magnetic Stimulation" with some minor modifications. TPMS will be performed at the Urology Suite, SCI section, I floor of the main hospital.

Our specific aims are:

- 1) To show feasibility of recruitment of prostate cancer survivors, acceptability of transpelvic magnetic stimulation (TPMS) intervention and retention of this Veteran population.
- 2) To test the feasibility of administering symptom scores in this population to detect severity and early recovery of functional impairment.
- 3) To test the feasibility of diagnostic imaging to establish: penile/pelvic floor muscle (PFM) blood flow, PFM anatomical and morphological changes before surgery, immediately after surgery, and after TPMS interventions.

Patient Recruitment: Our co-investigator, [name] will recruit patients from her urology clinic men over 50 years old who are enrolled for prostate surgery (n=20). After recruitment, 20 male patients will be assigned 1:1 to either age-matched control (G1; sham TPMS) or age-matched intervention (G2; TPMS) groups using computer-generated randomization, and baseline parameters (continence, sexual functions-using standadized questionnaires (please see attachments for reference), PRM, ICM and penile morphology- by MRI, blood flow- using laser Doppler measurement) will be established. All patients will be instructed ([name]) to perform standard of care pelvic floor exercise for the duration of the study. Patients will under go three month TPMS treatment every week (2-visits per week from 0-12 weeks as shown in Figure) starting when she feels the patient is ready for this treatment (after catheter removal). Patients will be evaluated (symptom score, MRI and blood flow) at baseline and at the end of the study (timeline attached). All enrolled patients will undergo TPMS treatment in addition to standard clinical- pelvic floor exercise. The study will be conducted after removal of the in dwelling catheter on patients who: had robotic assisted laparoscopic radical prostatectomy and have no evidence of metastasis and postoperative PSA < 0.2. The TPMS operator will not be blided but those analyzing the IIEF, IQIC scores, and evaluating Doppler blood flow and MRI findings will be blinded to the assignment.

Impact of COVID-19 Pandemic: Due to on-going COVID-19 pandemic, proposed timeline may be impacted due to the restrictions on human research. The scheduling for this research study will be based on availability of SCI suite for exclusive research study use when there are no other patients at that time. Research study patient will be the only patient in the suite at that time of the research study. All facility mandated santization and social distancing protocols will be strictly implemented and followed.

TPMS Treatment: Magnetic stimulation device MagVentrure's R30 (FDA approved for peripheral stimulation) that targets pelvic floor muscles will be used. We propose 10 Hz (for blood flow stimulation) and 30 Hz (for pelvic muscle strengthening), in an 8 seconds on- 4 seconds off

pulsing manner TPMS that encompass previously employed range of frequencies in humans for pelvic floor stimulation (based on published methodology -Lim et al, J Urol 197:1302, 2017, attached). Number of trains will be about 50. no of pulses in train would be about 240. Each cycle will be of total 20 minutes duration, followed by 20 min of coil cooling period before the second cycle. Based on our preliminary studies in 2 subjects for about 8 weeks, this protocol was well toleated. Both subjects felt the sensations at the high frequency 30 Hz. Same TPMS device will be used for the control (G1: sham) group, but with a sham magnetic coil. Sham coil is designed to provide <5% energy during sham TPMS. The treatment regimen will involve two 20minute sessions/visit and 2 -visits per week as follows: Weeks: 1, 2, 3, 4, 5, 6, 7, 8, 9, 10, 11, 12 (final monitoring at 24 weeks). TPMS will be administered by a trained clinical coordinator under the supervision of an urologist. The coordinator will not be involved in subject's assessment. We will apply first low amplitude (5%) to improve blood flow followed by high amplitude (30-50 %) TPMS, to strengthen muscles. Symptom scoring using questionarries and blood flow (Doppler) will be perfored at: baseline (before starting TPMS), and at weeks 4,8, 13, 24 after starting TPMS as shown in the atatched figure: IRB Methods: Timeline. At the initial visit, subjects will receive education about TPMS and anatomy and the role of TPMS in increasing pelvic blood flow and muscle strength. This protocol will allow us to quantify the direct beneficial effect of TPMS on muscle strengthening. Patients will also get standard clinical care and training for pelvic floor exercise.

Chair & Parameters Used: The coil will be placed on a chair manufactured by MagVenture with additional sponge to make the coil comfortable to sit on. This coil will be energized to provide magnetic stimulation at the identified amplitude, frequency and duration. The magnetic field generated during stimulation will subsquently stimulate the tissue in its field. Data Analysis & Interpretation:

Feasibility Outcomes: We will estimate: 1) Numbers of potentially eligible patients, number invited, number attending a pre-operative assessment clinic and consent rates (target recruitment is 24 or 3 participants per month over an initial 8-month recruitment period). 2) Patient concerns about the proposed therapy sessions/week and study duration. 3) Feasibility of recruiting in other clinics in which staff are interested in participating in a future main trial. 4) Retention, acceptability rates including response to treatment, questionnaires and imaging. 5) Intervention fidelity and adherence using study coordinator-completed case responses. 6) Determining the sexual function and continence improvement by assessing and comparing sensitivity to change. 7) Participant satisfaction with the interventions on a rating (Likert) scale. 8) Participant confidence to undergo a longer duration TPMS study. 9) Identification of barriers and enablers to adherence. 10) Establishment of outcome measures that best reflects the participants' rehabilitation goals.

Data Analysis & Interpretation: We will analyze qualitative interview data using atlas.ti, qualitative data analysis software, and the quantitative data using the SPSS version 24. We will start by coding, a process in which quotes are marked and labeled. The labeled quotes are then sorted and grouped, so that categories, then concepts, then themes can be developed. As is often standard practice for qualitative data analysis, analysis will be concurrent with data acquisition. Quantitative data will be examined initially for missing values. The primary aims of our data analytic strategy will be directed toward the adherence, retention and any guidance to inform modification of our method. We will focus our analyses on a feasibility of conducting a larger study and report our findings with this limitation in mind. Our goal is to collect important data regarding our method, our ability to implement recruitment strategies, and the feasibility of the treatment and measurements. Information derived from our research will lead to better-designed full-scale studies and informed decisions regarding whether it is worthwhile to commit additional resources to future treatment development. For quantitative data, descriptive statistics will be used to summarize the variables as well as detect outliers and data entry errors. When applicable, normality of the distribution will be examined for outcome variables. Chi-squared and Analysis of Variance will be used to assess the effectiveness of the randomization procedures by comparing participants in each treatment condition on baseline variables. Due to our small sample size our statistical analytical finding will be interpreted with caution. Other preliminary analyses will include evaluation of patterns of missing data, dropout rates, distributional properties of variables, and correlations among measures. Although there are important limitations associated with the analysis of our data, we do propose to conduct limited statistical analyses. First, keeping in mind the theoretical and practical issues reviewed above, all analyses will be considered preliminary. We will calculate an estimated effect size for our primary outcome, though it will be interpreted with caution, and in the context of the 95% confidence interval that surrounds it. It will also be interpreted within the context of other important information such as the clinical significance of study findings, and existing data from prior relevant research studies. For aims 2-3, All potential covariates (e.g., age, duration of cancer) will be summarized with descriptive statistics and graphs to determine whether a continuous, categorical, or interval representation is most appropriate. Second, effect of any systematic differences between dropouts and completers will be explored by including the variable of concern to the model as a covariate. Third, any comparison can be adjusted for subject-specific characteristics (e.g., covariates found in initial analyses). Furthermore, group by time interaction will be included in all models. For Aim 2-3, descriptive statistics and exploratory graphing such as frequencies, means, standard deviations, box and whisker plots, stem and leaf diagrams, and scatter plots will be used to assess normality of the data. If necessary, the continuous outcome data will be transformed appropriately. Prior experience leads us to expect that for all variables, the distributions will be skewed and the variances will not be homogeneous. Similarly, potential covariates will be summarized with descriptive statistics and graphs to determine whether a continuous, categorical or an interval representation is the most appropriate approach. Missing data will be examined to assess randomness. Analysis of variance will be used to test our hypothesis. We will adjust pvalues for multiple testing using a Bonferroni correction. Data will be analyzed using a Mixed Effect Model. This method allows the inclusion of subjects with missing data or those who terminated early without relying on data imputation procedures. Denominator degrees of freedom will be calculated using the Kenward-Roger small sample correction. Data will be analyzed from all randomized subjects for whom we have a baseline assessment and at least one post-baseline evaluation. Effect of these mediator variables will be tested using the same mixed model. To test for mediation effect, we will utilize the analytic strategy. The multiple-mediation model includes a multiple-path mediating effect through both mediators which allows one mediator to causally affect the other. We will conduct a Sobel testnto check for significant mediation. Next, we will use the formula provided by MacKinnon to determine the percentage of the intervention condition to primary outcome path that was accounted for by change in our mediator. Based on our ongoing studies, we expect a dropout rate of <10% after baseline assessment. Primary outcomes will be tested using an intent-to-treat framework. The data will be analyzed by a "Mixed Effect Model." As we mentioned above, due to our small sample size our statistical analytical finding will be interpreted with caution.

Possible Risks: Based on available literature (see references in section 7) it is unlikely that TPMS will result in any other complications suggested by the reviewer.

Abbreviations used in the figure/text: LSCI- Laser speckle contrast imaging; PW - Pad weight, rMS- Repetitive magnetic stimulation, TPMS- Transpelvic pelvic magnetic stimulation, UI - Urinary incontinence, UTE- Ultrashort echo time, UPP- Urethral pressure profile, LPP- Leak point pressure, HDM- High definition manometery, DTI- Diffusion tensor imaging and UTI-Urinary tract infections.

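### Do the TPMS train, pulse and cycle-length figures contradict one another?

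*Combined protocol and SAP*

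**What the plan says.** The TPMS Treatment paragraph of Section 9 sets two frequencies under one on/off pattern: "We propose 10 Hz (for blood flow stimulation) and 30 Hz (for pelvic muscle strengthening), in an 8 seconds on- 4 seconds off". It then gives the counts and the cycle length: "Number of trains will be about 50. no of pulses in train would be about 240. Each cycle will be of total 20 minutes". Cooling is separate from the cycle: "followed by 20 min of coil cooling period before the second cycle". Each visit has two 20-minute sessions, with two visits a week for 12 weeks. The order within treatment is given as "We will apply first low amplitude (5%) to improve blood flow followed by high amplitude (30-50 %) TPMS, to strengthen muscles". Section 7 repeats the counts in the same words ("Number of trains will be about 50. no of pulses in train would be about 240").

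Section 7 also separates the two purposes by amplitude. On blood flow it says "low intensity (5-10% amplitude) TPMS improves blood flow as shown in our laboratory", and on muscle "higher intensity (30-50% amplitude-based on the amplitude that results in patient feeling the muscle activity) helps muscle regeneration and function". Read with the frequency sentence, this pairs 10 Hz with low amplitude and 30 Hz with high amplitude.

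No visible sentence says whether the 50 trains are per frequency, per cycle or per visit, which frequency the 240 pulses belong to, or how the two phases divide a cycle.

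**The concern.** One train count and one pulse count are given for two frequencies, and read literally they cannot hold for both. At 10 Hz an 8-second train cannot contain 240 pulses, and 50 trains at the stated pattern occupy only half of a 20-minute cycle. The word about does not stretch to a threefold or twofold gap, and the cooling period comes after the cycle, so it does not account for the missing 10 minutes.

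TPMS is the only randomised component of the trial. The Chair & Parameters Used paragraph says "This coil will be energized to provide magnetic stimulation at the identified amplitude, frequency and duration", so a reader expects one identifiable set of values. If the set were truly inconsistent, two operators could program different treatments, and a later full-scale trial could not tell from the protocol what had been delivered. Intervention fidelity is among the listed feasibility outcomes, and the good tolerability reported in two preliminary subjects is attached to this same regimen.

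**Working it through.** **Inputs (Sections 7 and 9).** Frequencies 10 and 30 Hz; 8 s on and 4 s off; about 50 trains; about 240 pulses per train; 20-minute cycle; 2 cycles per visit; 2 visits per week; 12 weeks.

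**Pulses per train = frequency × on-time.**
- 30 Hz: 30 × 8 = 240. This reproduces the stated figure exactly.
- 10 Hz: 10 × 8 = 80. The stated figure is 240/80 = 3 times as large. Reaching 240 at 10 Hz would take 240/10 = 24 s of on-time, against the stated 8 s.

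**Trains per cycle = cycle seconds ÷ (on + off).**
- One train period is 8 + 4 = 12 s, and the cycle is 20 × 60 = 1,200 s.
- Capacity is 1,200/12 = 100 trains.
- Fifty trains take 50 × 12 = 600 s = 10 minutes.
- Spreading 50 trains over the whole cycle would mean 1,200/50 = 24 s per train, hence 16 s off, against the stated 4 s.

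**What the 50 could count.**

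| Unit of the 50 | Time used | Trains over the course |
|---|---|---|
| Per visit | 10 of 40 min | 24 visits × 50 = 1,200 |
| Per cycle | 10 of 20 min | 48 cycles × 50 = 2,400 |
| Per frequency within each cycle | 600 + 600 = 1,200 s, or 20 of 20 min | 48 × 100 = 4,800 |

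Visits are 2 × 12 = 24 and cycles are 24 × 2 = 48.

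**Does any reading satisfy every stated figure?** The third row does for time. It uses the 8/4 pattern, the 50 and the 20 minutes without remainder, and it follows the low-then-high order. The 240 then describes the 30 Hz trains, and the 10 Hz count of 80 follows from the stated frequency and on-time. Pulses per cycle would be 50 × 80 + 50 × 240 = 4,000 + 12,000 = 16,000. A total of 100 × 240 = 24,000 is not a rival reading, because it needs 10 Hz trains of 240 pulses in 8 s, which cannot occur.

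**Does anything downstream use these counts?** The feasibility outcomes in Section 9 list fidelity and adherence, assessed from forms completed by the coordinator, but name no train or pulse measure. The mixed model, the covariates and the planned 20 patients do not depend on them. Sessions, visits and minutes are stated and can be scored as they stand.

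**The case for a change.** The strongest reply is that the reconciling reading is inferred. Giving low amplitude in the first cycle of a visit and high amplitude in the second is just as natural a reading of the stated order, and then 50 trains leave half of each cycle unexplained. The IRB form asks for a precise account of what is done to subjects, the same unlabelled counts appear in two sections, and the remedy would cost a few words.

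Much of this stands. The text does not name the unit, the frequency or the phase split, and the good numerical fit does not prove intent. The exposure that the two preliminary subjects tolerated cannot be reconstructed from these sentences alone.

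What does not stand is the step from unlabelled to contradictory. A twofold gap in trains appears only if the 50 is taken as per cycle, which is the point in doubt; under the per-frequency reading there is none. Nor does the document show any decision, outcome or analysis that turns on the answer. Section 9 also describes the study as a previously approved protocol with minor modifications, and it refers to an attached published method and timeline figure; Section 7 refers to an attached user manual. Those may record the setting, though this cannot be confirmed from the text available here.

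**Conclusion.** The arithmetic behind the concern is right, but it does not establish an error. Both disputed figures can be recovered exactly from the plan's own inputs: 240 = 30 × 8, and 2 × 50 × 12 s = 20 minutes. What is left is incomplete labelling of two counts. Its size is a range of 1,200 to 4,800 trains over the course, set entirely by the unit of the 50, with 80 or 240 pulses per train according to frequency.

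No change to the plan follows. Frequency, pattern, cycle length and schedule are all stated. The sample size, randomisation, outcomes and analysis as written do not rest on a train or pulse count. The conclusion assumes continuous 8/4 pulsing through the cycle, and that no unseen attachment makes a train or pulse count a fidelity criterion. Which setting is delivered is for the investigators, and none is endorsed here. If they revise Sections 7 and 9 for other reasons, reconciling the two passages by adding the unit, the frequency and the phase split would be a courtesy to readers.
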